## **Lay Summary of Proposed Research**

### **Lay Summary of Proposed Research**

The purpose of this study is to explore the tolerability and effectiveness of transcranial direct current stimulation (tDCS) as a potential treatment for non-suicidal self-injury (NSSI). NSSI is the deliberate attempt to harm oneself, most often through cutting or burning, without suicidal intent. NSSI is a maladaptive emotion-regulation strategy often triggered by negative emotions, especially those involving feelings of rejection. tDCS is a low-cost, portable, well-tolerated, non-invasive form of brain stimulation that delivers a low current to a specific area of the brain via electrodes. Several studies have demonstrated its effectiveness in treating an array of conditions, depending on electrode placement, including depression and chronic pain. tDCS may also facilitate adaptive emotion regulation; researchers have also successfully used tDCS to reduce negative emotions and aggressive responses to social rejection. We therefore seek to explore tDCS as a potential treatment for NSSI. This pilot feasibility study seeks 1) to examine how tDCS is tolerated in a sample of individuals who engage in frequent NSSI; 2) to gather pilot data regarding changes in neural responses to social rejection after a series of tDCS sessions in this clinical population of individuals who engage in NSSI; 3) to gather pilot data on the effects of tDCS on NSSI behaviors and urges. A sample of up to 10 volunteers will pilot the social feedback task during fMRI to assess its feasibility before beginning fMRI procedures in our patient sample. This task will involve participants playing a virtual ball-tossing game with two cartoon characters over the computer. We seek to recruit a sample of 22 individuals who engage in frequent NSSI to complete all study procedures, including neuroimaging. Individuals will be randomized to receive active- or sham-tDCS for two twenty-minute applications on each of six alternating days over approximately two weeks. tDCS delivery using a remotely-supervised treatment protocol will minimize the burden of study visits and allow patients to continue participating in research from the comfort of their homes when in-person procedures are not possible. During tDCS, participants will listen to an audio file with different sounds and a voice instructing them to switch their attention between the different sounds. The fMRI task will be performed at baseline and again after the completion of 12 sessions of tDCS. Subjects' NSSI and urges to engage in NSSI will be recorded for three weeks in real-time, using an iPod- based system that reminds subjects to stop at certain times during the day to record their

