## Specific Aims and Hypotheses

### Specific Aims and Hypotheses

Aims/Hypotheses 1 through 3 pertain to the sample of patients with NSSI. Aim 4 pertains only to the non-clinical sample who will pilot our social feedback task. Aim 5 pertains to the remotely-supervised no-contact arm of the study.

1. Evaluate the tolerability and acceptability of a tDCS intervention in a sample of individuals engaging in frequent NSSI. We hypothesize that 6 treatments of tDCS (two times per day for three days over right vLPFC) will be well-tolerated by study participants who engage in frequent NSSI.
2. Characterize changes in BOLD responses to social rejection from pre- to post-tDCS sessions in the active tDCS group compared to the sham tDCS group using fMRI and a social exclusion task called Cyberball. Hypothesis: BOLD activity in the dorsal anterior cingulate cortex, the anterior insula, the amygdala, and the medial PFC/rostral ACC will scale with different percentages of exclusion in Cyberball. Furthermore, there will be a significant interaction effect whereby participants in the sham stimulation group will show greater changes in these three regions during scan 2 compared with those in the active group.
3. Gather pilot data on the effectiveness of tDCS in treating NSSI and the urge to engage in NSSI in patients currently suffering from NSSI on a regular basis. Hypothesis: tDCS directed to the right ventrolateral prefrontal cortex will lead to greater reductions in both NSSI and in urges to engage in

NSSI, as assessed by self-report measures as well as real-time monitoring using ecological momentary assessment, than sham tDCS.

4. Assess feasibility of the behavioral and neural responses to a social feedback task in a non-clinical sample.
5. Assess the feasibility of using remotely-supervised tDCS self-administration in a sample of patients who engage in NSSI.

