#### **Patients with NSSI undergoing tDCS and fMRI:**

Our sample will be defined by a symptom/pattern of behavior, and not by a DSM-V diagnosis. Specifically, we seek to recruit individuals engaging in frequent NSSI, because that is the symptom that we will attempt to target with this treatment. We aim to recruit 22 subjects who complete all study procedures. Based on recent brain imaging studies in our division, we estimate that we will need to enroll 50 subjects to achieve this number of completers, due to subject ineligibility, subject withdrawal prior to study completion, and failure to attend appointments.

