## **STATISTICAL ANALYSIS PLAN**

This is a double-blinded, randomized, sham-controlled pilot study examining the tolerability and effectiveness of repeated administrations of tDCS over right vIPFC in treating NSSI and its underlying neural correlates.

Primary analyses on behavior and clinical outcomes will be conducted using linear mixed effects models to account for repeated measures over time and individual variability. All tests will be performed using two-sided alternatives with alpha=0.05. Ecological momentary assessment data will be evaluated using mixed effects logistic regression. BOLD imaging data will be analyzed using generalized linear models comparing pre- and post- intervention neural responses to inclusion and exclusion trials during the Cyberball game. For all analyses, we will examine standard diagnostic plots to identify evidence of lack of model fit, presence of outliers or overly influential points, etc., and take appropriate remedies as indicated (e.g., review source data of outliers, transform data, etc.).

As this is a pilot study, additional exploratory analyses will be conducted for hypothesis generating purposes.

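### The SAP does not say how the BOLD model links each person's two scans, and it does not adjust the arm comparison for the scan-1 response

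*Combined protocol and SAP*

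**What the plan says.** The Statistical Analysis Plan gives imaging one sentence: "BOLD imaging data will be analyzed using generalized linear models comparing pre- and post- intervention neural responses to inclusion and exclusion trials" during Cyberball. It states no subject effect, paired contrast, covariance structure or scan-1 covariate, and does not mention arm.

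In the same paragraph, behavioural and clinical outcomes get "linear mixed effects models to account for repeated measures over time and individual variability", and "Ecological momentary assessment data will be evaluated using mixed effects logistic regression". The general testing rule is "All tests will be performed using two-sided alternatives with alpha=0.05".

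The Lay Summary fixes the number of scans: "The fMRI task will be performed at baseline and again after the completion of 12 sessions of tDCS". Under Specific Aims and Hypotheses, Aim 2 is to "Characterize changes in BOLD responses to social rejection from pre- to post-tDCS sessions in the active tDCS group compared to the sham tDCS group", and its second hypothesis is that "there will be a significant interaction effect whereby participants in the sham stimulation group will show greater changes". On size, the description of the fMRI sample says "We aim to recruit 22 subjects who complete all study procedures"; the Background section gives 23.

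**The concern.** Two scans of one person are correlated, and Aim 2 concerns the change between them. The SAP handles this kind of dependence explicitly for the clinical outcomes and names a mixed model for the EMA data. For BOLD it names a model class that, in its basic form, assumes independent rows, and it adds nothing about the pairing. The group-level model is therefore left to be chosen later, and the options differ materially in precision.

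Aim 2 has about 11 scan pairs per arm. An analysis that ignores the pairing reports too wide an interval for the change contrast. One that pairs the scans by subtraction is valid, but leaves precision unused that the baseline scan, already collected, would supply.

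**Working it through.** **No figure to reproduce.** The documents give no power, SD, effect size or scan-to-scan correlation for BOLD.

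**Inputs from the documents:** two scans per person (Lay Summary); 22 completers (fMRI sample description); two-sided alpha 0.05 (SAP); an arm-by-scan contrast (Aim 2).

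**Assumptions:** 1:1 allocation, so n = 11 per arm; equal SD s at both scans and in both arms, set to 1; correlation r between one person's two scans of 0.3, 0.5 or 0.7.

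**Variance of the active-minus-sham effect**

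- Scans treated as independent rows (the variance the model would report): 4s²/n = 4/11 = 0.364.
- Within-person change: 4s²(1−r)/n.
- Scan 2 adjusted for scan 1: 2s²(1−r²)/n, times 1 + 1/(2n−4) = 19/18 for estimating the slope in 22 people.

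| | r = 0.3 | r = 0.5 | r = 0.7 |
|---|---|---|---|
| Independent rows | 0.364 | 0.364 | 0.364 |
| Change score | 0.255 | 0.182 | 0.109 |
| Scan-1 adjusted, before slope factor | 0.165 | 0.136 | 0.093 |
| Scan-1 adjusted, with slope factor | 0.175 | 0.144 | 0.098 |

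**If the scans were independent rows.** With balanced data the point estimate equals the paired change contrast; only the reported SE differs. It is too large by 1/√(1−r): 1/√0.7 = 1.20, 1/√0.5 = 1.41, 1/√0.3 = 1.83. The normal approximation to the actual size of the 5% test, 2(1−Φ(1.96/√(1−r))), gives 1.9% / 0.6% / 0.03%. Simulating 11 per arm with a t reference on 40 df gives about 2.1% / 0.7% / 0.1%. The simulated values are the ones to use, because the approximation is poor in the far tail.

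**If the scans are correctly paired.** The change-score test holds its level (simulated 5.0%). Its variance relative to the adjusted comparison is [2/(1+r)] × 18/19:

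- r = 0.3: 1.538 × 18/19 = 1.46
- r = 0.5: 1.333 × 18/19 = 1.26
- r = 0.7: 1.176 × 18/19 = 1.11

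Simulation gives 1.45 / 1.27 / 1.11, the same within simulation error.

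**What this means for power.** For an assumed true difference of 1 SD:

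| | r = 0.3 | r = 0.5 | r = 0.7 |
|---|---|---|---|
| Independent rows | 34% | 32% | 29% |
| Change score | 47% | 61% | 82% |
| Scan-1 adjusted | 62% | 71% | 86% |

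**Where the adjustment stops paying.** The adjusted variance is the smaller one while 2/(1+r) exceeds 19/18, that is, for r below 36/19 − 1 = 0.89.

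**The case against.** The strongest reply is that the SAP is silent and has not made an error. A reader might infer that it treats the two scans as independent, so that its error bars are wrong and scan 1 goes unused. The documents do not support that. Nothing states independence. Comparing pre with post is compatible with a per-person contrast carried to a group-level model, and Aim 2 speaks of changes from pre to post, which reads naturally as within-person change. Such an analysis gives valid error bars, and scan 1 enters it by subtraction. The mixed-model wording for the other outcomes shows uneven detail, not a decision to ignore pairing. All of this stands.

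A reader might also fear false positives. For the Aim 2 contrast with one row per scan, the error runs the other way: the test is conservative and loses power. Pooling many trial or block rows over people could make the SE too small, but the documents do not say that this is planned and give no variance components from which to size it.

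It can further be said that choosing the covariate over a change score is a preference between two valid analyses, that imaging here is pilot work, and that the SAP applies the word primary to behaviour and clinical outcomes. That limits the urgency. It does not remove the gain, which comes from data already collected.

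**Conclusion.** The point holds as a gap in specification plus an available gain in precision. The size of the gap depends on which reading is implemented. Independent rows would widen the SE by 20% to 83% over the assumed range and make the test strongly conservative. Correct pairing leaves only the 11% to 45% excess variance over the scan-1-adjusted analysis.

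These sizes rest on the assumed correlations, 1:1 allocation and equal SDs; the power figures also rest on the assumed 1 SD effect. With 23 completers in place of 22, the SEs change by about 2%. The case for stating the link between scans rests on none of these assumptions. The case for the covariate needs only a scan-to-scan correlation that is not close to 1.

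**What to change.** Keep the first-level modelling of inclusion and exclusion trials, including a test of Aim 2's first hypothesis, that BOLD scales with the percentage of exclusion. Then add a group-level specification for the arm comparison:

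1. For each person, scan and prespecified region, compute one exclusion-related response from the first-level model, and define that contrast in the SAP.
2. For each region, fit a linear model of the scan-2 response on arm and the scan-1 response, one row per person.
3. Report the adjusted active-minus-sham difference with a t-based 95% CI.

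The regions must be reconciled first. The Background section names three (anterior insula, dorsal anterior cingulate, amygdala). Aim 2 names four, adding medial prefrontal/rostral anterior cingulate, and then refers to three.

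One row per person removes the dependence problem in either direction, and writing arm into the model supplies the comparison that Aim 2 asks for. The cost is SAP wording and one residual degree of freedom for the slope (19 instead of 20 with 22 people). No new data or procedures are needed. The healthy-volunteer pilot, in which up to 10 people do the task in two scans at least 5 days apart, could give a rough check on the assumed correlation.

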### **Cyberball:**

Participants will be presented with animated drawings depicting the participant's avatar and two other 2 cartoon figures tossing a ball between each other and the participant. When the participant's avatar receives the ball, they will press one of two buttons indicating which of the other two cartoons will receive the ball next. The number of times the ball is tossed to the participant will vary each block, such that the participants feel excluded from the game to varying degrees. Participants will be told before the study that the other characters are not real people and that they are not really playing the game with other people, but asked to imagine it as though it were real. At the end of each scan, an investigator will check in with the participant

---

to make sure the task did not cause significant, lasting distress. If the participants are upset following the task, a clinician will be available to speak with the participant. After scan 2, the check-in will include a full debriefing about the purpose of the task, including an explanation that Cyberball is a simulation of social exclusion. During debriefing, participants will be reminded that the task was only a computer game and the other players were not real people.

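### Aim 2 predicts that BOLD scales with the percentage of exclusion, but the SAP's only imaging comparison uses two trial categories and so, as written, does not test scaling or use the graded task

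*Combined protocol and SAP*

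**What the plan says.** **Protocol, Specific Aims and Hypotheses, Aim 2.** There are two hypotheses. The first concerns the task response: BOLD in the dorsal anterior cingulate, anterior insula, amygdala and medial prefrontal/rostral cingulate cortex "will scale with different percentages of exclusion in Cyberball". The second concerns treatment, as an interaction in which "participants in the sham stimulation group will show greater changes in these three regions during scan 2" compared with the active group.

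**Protocol, Study Procedures, Cyberball.** Exposure is graded by block: "The number of times the ball is tossed to the participant will vary each block", so that participants "feel excluded from the game to varying degrees". The number of levels, their spacing and the number of blocks at each level are not given.

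**SAP.** The imaging analysis is one sentence. It names the model family, "BOLD imaging data will be analyzed using generalized linear models", and what is compared: "comparing pre- and post- intervention neural responses to inclusion and exclusion trials during the Cyberball game". It mentions no percentage-of-exclusion regressor, trend contrast or parametric modulator, and does not say how graded blocks relate to inclusion and exclusion trials.

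**The concern.** The aim and the task agree with each other: one predicts a dose-response and the other delivers graded doses. The analysis sentence matches neither, because it describes the response in two categories.

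Two things are at stake. First, an analyst who follows the SAP as written finishes without a test of the first Aim 2 hypothesis. Second, the information in the intermediate degrees of exclusion goes unused, both for the task response and for the pre-to-post comparison built on it. This is more than brevity, since the sentence does state what will be compared and that is not a slope. The general allowance for exploratory analyses at the end of the SAP does not close the gap: those are for generating hypotheses, and scaling is already one of the stated hypotheses.

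**Working it through.** The documents give no effect size, standard deviation or power figure for imaging, so there is no figure to reproduce. The check is a comparison of texts plus illustrative arithmetic.

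**Step 1. What each passage requires**

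| Place | Quantity |
|---|---|
| Aim 2, first hypothesis | Change in BOLD per unit of exclusion, within a scan |
| Cyberball procedure | Several degrees of exclusion, by block |
| SAP imaging sentence | Response to two trial types, pre versus post |

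The SAP quantity differs from the first row in two ways: it has two categories rather than a gradient, and it compares scans rather than levels within a scan.

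**Step 2. Can a two-category contrast show scaling?** Assume four equally spaced levels, split two and two.

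- Linear response (0, 1/3, 2/3, 1): upper mean 5/6, lower mean 1/6, contrast 4/6 = 0.667.
- Step response (0, 0, 2/3, 2/3): upper mean 2/3, lower mean 0, contrast 0.667.

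The contrasts are identical, so the comparison cannot separate scaling from a threshold. In design terms, intercept plus category has rank 2, and adding the percentage raises it to 3. The slope within categories is therefore not estimable from the two-category model.

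**Step 3. Size of any loss of information.** Assumptions, none of them in the documents: k equally spaced, equally frequent levels, and a truly linear response. With centred unit-spaced levels x, the sum of squares is k(k² − 1)/12.

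- Two-way split as near to half as possible: the share of slope information kept is the squared correlation of the split with x. This is 0.75 × k²/(k² − 1) for even k and 0.75 for odd k.
- Extremes only: (k − 1)² / (2 × k(k² − 1)/12) = 6(k − 1)/(k(k + 1)).

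| k | Split keeps | Extremes only keeps |
|---|---|---|
| 2 | 100% | 100% |
| 3 | 75% | 12/12 = 100% |
| 4 | 0.75 × 16/15 = 80% | 18/20 = 90% |
| 5 | 75% | 24/30 = 80% |
| 6 | 0.75 × 36/35 = 77% | 30/42 = 71% |
| 8 | 0.75 × 64/63 = 76% | 42/72 = 58% |

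For 3 to 8 levels, a split loses about 20-25%, and an extremes-only contrast loses from 0% to about 42%.

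**Step 4. Group level.** The variance of a participant's estimated slope is τ² + v, where τ² is between-person variance and v is within-person error. Keeping a share e of the information changes this to τ² + v/e. The ratio (τ² + v)/(τ² + v/e) is nearer to 1 than e whenever τ² > 0, so the loss in a group test or arm comparison is smaller than the table shows. The documents give neither variance, so the amount is unknown.

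**The case against.** **The SAP does not forbid a graded analysis.** A generalized linear model can carry a parametric modulator, and the sentence defines neither a contrast nor an endpoint. This stands. A reader might infer that the plan commits to a binary endpoint and rules out a scaling test, but the documents do not support that. What they support is that the comparison described does not test scaling and no other imaging analysis is named.

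**A trial may be a single toss.** The Cyberball procedure grades blocks, whereas the SAP speaks of trials, a term the documents do not define. If a trial is one toss, each toss either goes to the participant or does not. Two categories then arise naturally, and a graded block is a particular mix of them. This also stands. A reader might infer that the analyst is forced to cut partly excluded blocks into two groups, or to choose that cut after seeing the data. The documents say neither. The toss-level reading does not rescue the scaling hypothesis, however: a toss-level contrast pooled over blocks is still not a slope on percentage of exclusion.

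**The treatment hypothesis is still served.** Aim 2's central question is the change in response to rejection, active versus sham. An inclusion-versus-exclusion contrast can address it, so it would be wrong to infer that the target-engagement comparison is invalid.

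**This is a pilot.** That limits how serious the gap is. It does not remove it, since the protocol's background says the work may lead to larger trials of target engagement.

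**Conclusion.** The point holds in a limited form. Aim 2 states a scaling hypothesis, the task is graded to match, and the SAP's only imaging comparison neither tests that hypothesis nor uses the grading. This conclusion rests on the text and on Step 2 of the working, not on the efficiency figures.

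The size of any loss of precision cannot be fixed from the documents. The percentages in the working depend on an assumed number of levels, equal spacing, equal frequency and linearity. They describe within-person information only, and they do not apply if trials are single tosses. A reader might take one narrow range from that table as the loss in this trial; it is not a bound, since even the cases shown run from none to about 42%.

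The change is worth making before the imaging data are analysed, but the gap does not undermine the trial's tolerability or clinical aims.

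**What to change.** Revise the SAP's imaging text as follows.

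1. State the exclusion levels (percentage per block and number of blocks at each) and define an inclusion trial and an exclusion trial, as tosses or as blocks.
2. Add percentage of exclusion per block to the first-level model as a parametric modulator, or as an ordered block factor with a linear trend contrast.
3. For the scaling hypothesis, test that slope against zero at scan 1 in the Aim 2 regions. List the regions: the first hypothesis names four, while the interaction hypothesis refers to three.
4. For the treatment hypothesis, test the arm-by-scan interaction on the slope alongside the planned inclusion-versus-exclusion contrast. The imaging sentence does not mention arm, so write the interaction out.
5. Name in advance which of the two measures, slope or contrast, is the main one. They answer different questions (sensitivity to degree of exclusion, and response to exclusion), and either choice is defensible if made beforehand.

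The cost is a few sentences in the SAP and one first-level regressor, with no new data or visits. The small downside is a linearity assumption, which the retained contrast or the ordered factor helps to check, and one more contrast to report.
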